4.2.3 Exploratory Endpoint(s) and Analyses

CCI

CCI

4.2.4 Safety

The population used for safety analyses will be the safety analysis set (SAF).

4.2.4.1 Patient Disposition

Patient disposition will be presented overall. Tabulation will include the number of patients screened, number of patient's screen failed, number of patients with inclusion criteria not met, number of patients with exclusion criteria met, number of patients enrolled, number and percentage of patients in safety analysis sets, as well as the number and percentage of patients discontinuing study treatment and the reason for treatment discontinuation. In addition, this table will summarize the number and percentage of patients discontinuing the study and the primary reason for study discontinuation. The number of patients enrolled will be used as denominator for calculating the percentages.

Listings will be provided for patient disposition, and patients with inclusion criteria not met and exclusion criteria met.

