2.2 Background

The PACIFIC study was a randomized, placebo-controlled, Phase 3 trial evaluating the immune checkpoint inhibitor durvalumab in patients with unresectable Stage III NSCLC who did not have disease progression after 2 or more concurrent cycles of platinum-based chemoradiotherapy. At the first planned interim analysis, the trial showed that durvalumab treatment significantly prolonged progression-free survival, as compared with placebo, with median durations of 16.8 months (95% confidence interval [CI], 13.0 to 18.1 months) and 5.6 months (95% CI, 4.6 to 7.8 months), respectively ([Antonia et al. 2017](#)). On the basis of these results, durvalumab treatment was approved by the United States Food and Drug Administration (US FDA) for the treatment of unresectable Stage III NSCLC in patients whose disease had not progressed after platinum-based chemoradiotherapy. In addition, overall survival was found to be significantly prolonged in durvalumab-treated patients compared with the placebo group (stratified hazard ratio for death, 0.68; 99.7% CI, 0.47 to 0.997; $p=0.0025$) ([Antonia et al. 2018](#)). During the PACIFIC trial, pneumonitis or radiation pneumonitis of any grade occurred in 33.9% and 24.8% and Grade 3 or 4 pneumonitis or radiation pneumonitis occurred in 3.4% and 2.6% of durvalumab and placebo patients, respectively ([Antonia et al. 2017](#)). A total of 15.4% of patients in the durvalumab arm discontinued study drug due to AEs, compared with 9.8% in the placebo arm ([Antonia et al. 2018](#)). The most frequent AEs leading to study drug discontinuation were pneumonitis (4.8% in the durvalumab group and 2.6% in the placebo group), radiation pneumonitis (1.3% in both groups), and pneumonia (1.1% in the durvalumab group and 1.3% in the placebo group). Immune checkpoint-inhibitor-related pneumonitis is a potentially serious and life-threatening toxicity. The reported incidence of pneumonitis in studies investigating anti-programmed cell death 1/programmed cell death-ligand 1 is variable and ranges from 0% to 10%, with an overall incidence of 2.7% reported in a recent meta-analysis of 20 studies with programmed cell death 1 (PD-1) inhibition; the incidence in patients with lung cancer as the underlying diagnosis is even higher ([Nishino et al. 2016](#)).

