3.2 Study Endpoints

The endpoint used to address the primary objective is:

- Occurrence of pneumonitis (either radiation or immune-mediated, by grade).
 - Grade of pneumonitis at diagnosis and highest grade of pneumonitis

The endpoints used to address the secondary objectives are:

- Occurrence of pulmonary AEs, including diagnoses of events, by grade
- Duration (days) of pulmonary AEs by type and grade
- Permanent discontinuation of durvalumab due to pulmonary AEs, including pneumonitis
- Early discontinuation of durvalumab treatment for any reason
- Duration (days) of durvalumab treatment
- Treatment interruptions, duration (days) of interruptions, and the reason for interruptions that will be captured in a standard data management form with the site physician documenting reasons in patient charts
- Time (days) to development of Grade 3 to 5 AEs, including pneumonitis

- Prescription of medication used to manage pulmonary AEs and duration (days) of treatment
- Change in QoL scores from baseline

The endpoints used to address the exploratory objectives are:

CCI

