9.3.1 Efficacy Analyses

PRO values and values from the mobile technology will be considered in connection with events of interest, specifically pneumonitis. Contributions to the identification/prediction of pneumonitis from PROs and variables collected by the devices may be assessed using regression models (e.g. logistic regression) depending on the number of events of interest that are observed in the study; the primary endpoint in these estimations will be the occurrence of pneumonitis. Lagged PRO values and values collected from the mobile technology may be incorporated as covariates in these models; more details will be specified in the SAP. The analyses of the primary endpoint will be conducted by overall patients in the full analysis set (FAS).

Continuous secondary and exploratory endpoints (e.g., duration of durvalumab treatment, duration of pulmonary AE, and absolute QoL and its change from baseline) will be summarized by the number of observations, mean, standard deviation, median, minimum, maximum, and 95% CIs. Categorical variables will be summarized by frequency counts, percentages, and 95% CIs for each category. All descriptive statistics of secondary and exploratory endpoints will be conducted by overall patients in the FAS.

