2. ANALYSIS SETS

2.1 Definition of Analysis Sets

2.1.1 Safety Analysis Set

The Safety Analysis Set (SAF) will include all enrolled patients who take at least 1 dose of durvalumab.

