4.2.2.3 Permanent discontinuation of durvalumab due to pulmonary AEs, including pneumonitis

This endpoint is fulfilled by section 4.2.4.1 patient disposition.

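### The durvalumab discontinuation endpoints are left to a disposition table that divides by enrolled patients, specifies no confidence interval and plans no pulmonary summary

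*SAP*

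**What the plan says.** The protocol (3.2) names as a secondary endpoint "Permanent discontinuation of durvalumab due to pulmonary AEs, including pneumonitis", and separately early discontinuation for any reason. The first of these answers the first secondary objective in protocol 3.1.

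SAP 4.2.2.3 consists of one sentence: "This endpoint is fulfilled by section 4.2.4.1 patient disposition". SAP 4.2.2.4 says the same for any-reason discontinuation. The disposition table in 4.2.4.1 gives the "number and percentage of patients discontinuing study treatment and the reason for treatment discontinuation", and states that "The number of patients enrolled will be used as denominator for calculating the percentages". It names no pulmonary or pneumonitis category, does not refer to the term lists in SAP 8.2 and 8.3, and does not mention a confidence interval.

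Other passages point elsewhere:

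- Protocol 9.3.1 puts all secondary endpoints on the FAS, which protocol 9.2 restricts to patients with at least one dose. It adds: "Categorical variables will be summarized by frequency counts, percentages, and 95% CIs for each category".
- SAP 6 drops the FAS, but does not say that enrolled patients replace it for any endpoint.
- SAP 4.2.4, the parent of the disposition section, names the SAF, and SAP 2.1.1 defines it: "The Safety Analysis Set (SAF) will include all enrolled patients who take at least 1 dose of durvalumab".
- SAP 4.2.2.5 summarises duration of durvalumab in the SAF.
- SAP 4.2.4.8 plans a listing of AEs that led to stopping durvalumab. No summary of them is among its AE tables.

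**The concern.** An enrolled denominator is normal in a disposition table. The difficulty is that the same table is asked to serve as the analysis of two endpoints, and it was not built for that.

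- **Population.** Protocol 4.1 has patients enrolled before they start durvalumab. A patient who is enrolled but never dosed cannot discontinue the drug, yet counts in the denominator. Two closely related endpoints, duration and discontinuation, would then rest on different populations without explanation.
- **Precision.** Few events are expected, so the percentage alone says little.
- **Definition.** SAP 4.2.2.1 defines pulmonary AEs so that pneumonitis is excluded. The discontinuation endpoint covers both, so it needs the 8.2 and 8.3 lists together, and nothing in the SAP says to combine them here.

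At stake is the reading of a secondary endpoint that protocol 4.2 includes among the factors for moving to a larger trial. Without a stated attribution rule, which discontinuations count as pulmonary would be settled after the data are seen.

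**Working it through.** **Inputs.** Planned size 75 (protocol 9.1). For the durvalumab arm of the cited Phase 3 trial, protocol 2.2 states: "A total of 15.4% of patients in the durvalumab arm discontinued study drug due to AEs". The same section gives discontinuation due to pneumonitis 4.8%, radiation pneumonitis 1.3% and pneumonia 1.1%. The number of enrolled patients never dosed is not in the documents and is an assumption below.

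**1. Reproduce the plan's own figures.** Protocol Table 4 uses exact Clopper-Pearson limits for x events in n = 75:

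- lower limit = 2.5% quantile of Beta(x, n − x + 1)
- upper limit = 97.5% quantile of Beta(x + 1, n − x)

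For x = 5 this gives 6.7% (2.2%, 14.9%), and for x = 12 it gives 16.0% (8.6%, 26.3%). All 12 rows of the table are reproduced to one decimal.

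**2. Expected number of pulmonary discontinuations.** Pneumonitis plus radiation pneumonitis: 4.8% + 1.3% = 6.1%, if no patient is counted under both. 75 × 0.061 = 4.6, about 5 patients.

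**3. Denominator effect, with 5 events.**

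| Assumption | Enrolled denominator | Dosed denominator (exact 95% CI) |
|---|---|---|
| 75 enrolled, 2 never dosed | 5/75 = 6.7% | 5/73 = 6.8% (2.3%, 15.3%) |
| 75 enrolled, 5 never dosed | 5/75 = 6.7% | 5/70 = 7.1% (2.4%, 15.9%) |
| 75 enrolled, 10 never dosed | 5/75 = 6.7% | 5/65 = 7.7% (2.5%, 17.0%) |
| 80 enrolled, 75 dosed | 5/80 = 6.3% | 5/75 = 6.7% (2.2%, 14.9%) |

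The shift runs from about 0.2 to 1.0 percentage points. The interval for 5/75 is 14.9 − 2.2 = 12.7 points wide, so leaving out the interval costs the reader more than the denominator does.

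**4. Effect of not separating pulmonary AEs.** This applies only if the CRF records one generic adverse-event reason.

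- Any AE: 75 × 0.154 = 11.6, about 12 patients, 16.0% (8.6%, 26.3%).
- Against pneumonitis plus radiation pneumonitis: 15.4 / 6.1 = 2.5.
- Adding pneumonia: 6.1% + 1.1% = 7.2%, 75 × 0.072 = 5.4 patients, and 15.4 / 7.2 = 2.1.

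The two ratios bracket a choice the documents leave open. Pneumonia without qualification is not on the 8.2 or 8.3 list, but it is a pulmonary AE in the ordinary sense. Protocol 2.2 reports only the most frequent causes, so further pulmonary causes would lower the ratio. Overlap between the summed categories would raise it.

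**5. Interval.** SAP 4.1 has a general rule that percentages get Clopper-Pearson intervals where suitable. SAP 4.2.1 and 4.2.2.1 repeat the interval explicitly for their percentages. SAP 4.2.4.1 does not, and SAP Table 1, which lists outcomes with their methods, contains interruptions but not discontinuation.

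**The case against.** The strongest reply is that the endpoint can still be recovered. The listing in SAP 4.2.4.8 shows every AE that led to stopping durvalumab, AEs are coded by preferred term, and about 5 cases are expected. Elsewhere the SAP plans listings when events are few, and the study is descriptive. This stands as far as it goes: a reader might infer that the pulmonary discontinuations cannot be obtained at all, and that is not so. But SAP 4.2.2.3 names the disposition table, not the listing, and a hand count from a listing has no stated rule for which terms qualify.

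Three other inferences also go too far.

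- A reader might conclude that the table will overstate the endpoint about 2.5-fold. The CRF reason categories are not shown. Since the SAP says the table fulfils a pulmonary endpoint, a breakdown that separates pulmonary events is possible. The ratio is conditional, and 6.1% covers only part of the endpoint.
- A reader might conclude that the SAP rules out an interval. The general rule in SAP 4.1 could be read to supply one. The accurate statement is that none is specified for these endpoints.
- A reader might conclude that the enrolled denominator distorts the result materially. Inclusion criterion 4 expects at least one dose, so few never-dosed patients are likely. Patients replaced after dosing stay in both counts. The table also prints the SAF count, so the percentage can be recomputed.

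**Conclusion.** The point holds. Two secondary endpoints are assigned to a table whose denominator differs from the protocol's dosed population and from the SAF used for treatment duration, and SAP 6 does not declare this. No interval is specified for either endpoint, although protocol 9.3.1 calls for one. The pulmonary endpoint has no planned summary unless the unseen CRF categories supply it.

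The denominator matters little numerically: up to about 1 percentage point for an assumed 10 never-dosed patients among 75. The missing pulmonary definition matters more. If the reason is generic, the table could show roughly 2 to 2.5 times the pulmonary rate, given the Phase 3 percentages and no overlap between categories. The any-reason endpoint is affected only through denominator and interval. For that endpoint the table otherwise does its job.

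**What to change.** - **SAP 4.2.2.3:** replace the pointer with a definition. Count SAF patients whose durvalumab was permanently discontinued because of an AE with an 8.2 term, with an 8.3 term, and with either, each patient once per row. Report n/SAF, percentage and exact 95% Clopper-Pearson interval.
- **SAP 4.2.2.4:** report any-reason discontinuation on the SAF, with the exact 95% interval.
- **SAP 4.2.4.1:** keep the enrolled denominator for the disposition table itself.
- **SAP 6:** record that these endpoints use the SAF in place of the protocol's FAS.

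The cost is one extra table. No new data are needed: protocol 8.3.1.3 already collects the action taken with durvalumab for AEs, and protocol 7.4.6 collects the reasons for permanent discontinuation.

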4.2.4.2 Demographic and Other Baseline Characteristics

Demographic and baseline characteristics will be standardized and summarized. Descriptive statistics will be presented for variables including age, age group, sex, height, weight, body mass index (BMI), oxygen saturation (SPO2 median from Current Health), etc. at baseline. All demographic and physiological data at baseline will be listed.

The following conventions will be used to standardize measurements for reporting purposes:

- Height (in cm) = height (in inches) * 2.54
- Weight (in kg) = weight (in lbs) * 0.4536
- BMI (kg/m²) = weight (kg)/ [height (m)²]
- Temperature (in °C) = 5/9 (Temperature [in °F] - 32).

4.2.4.3 NSCLC Disease History/Respiratory Disease History

NSCLC disease history will be listed including stages at diagnosis, referral, prior to treatment and study entry, histological grade and date of diagnosis.

Prior NSCLC treatment including radiation therapy with the time since last prior radiation and chemotherapy will be listed. In the radiation therapy, regimen, anatomical site, nodal station, duration of dose (days), total number of fractions, total doses, time since last prior radiation

and time since last prior radiation by intervals (< 14 days, 14 – 28 days, 29 – 42 days, 43 – 60 days, > 60 days) will be summarized.

Duration of Dose (day) = date of last dose – date of first dose +1.

Time since last prior radiation (day) = date of last dose of prior radiation – date of Day 1.

Surgical history and relevant previous respiratory procedures collected in CRF will be also presented in the listing.

4.2.4.4 Medical History and Concomitant Diseases

Medical History as recorded at baseline will be summarized overall using the number and percentages of patients reporting each system organ class (SOC) and preferred term (PT).

Medical history will be sorted by international order for SOC and in alphabetical order for PT using the Medical Dictionary for Regulatory Activities (MedDRA) coding dictionary version 22.1 or later in the summary table.

4.2.4.5 Prior and Concomitant Medications

Prior medications are medications taken before baseline and include medications ongoing at the start of durvalumab. Concomitant medications are medications taken on or after baseline. For medications with incomplete end dates, the imputed dates will be used to determine if the medications are concomitant. If a patient has taken a medication more than once, the patient will be counted only once in the total.

The summary of medications taken during the course of the study will be presented in tabular form using Anatomical Therapeutic Chemical (ATC) classification level 2 and generic drug name via the WHO Drug Global B3 Sep 2019 or later. All medications will be sorted alphabetically by ATC level 2 class and generic drug name. A listing of concomitant medications will be presented.

Concomitant procedures collected in CRF will be also presented in the listing.

4.2.4.6 Extent of Exposure

Durvalumab administration, dose assigned date, total dose and the reason for dose not taken will be presented in the listing.

4.2.4.7 Compliance Rates for PROs, spirometry, and wearable device

Summary measures of overall compliance and compliance over time will be derived for the spirometry, oximetry (referred to as measurement below) from the wearable device, EORTC-QLQ-C30 and LC13 (referred to as questionnaire below) respectively. These will be based upon:

- Expected measurement/questionnaire = a measurement/questionnaire that is expected to be completed at a scheduled assessment time e.g., a measurement/questionnaire from a patient who has not withdrawn from the study at the scheduled assessment time. Date of study exit will be mapped to the nearest visit date to define the number of expected forms. The schedule assessment time points for spirometry and oximetry are daily from Day 1 until date of study exit. The schedule assessment time for EORTC-QLQ-C30 and LC13 are described in 4.2.2.9.
- **CCI** [REDACTED]
[REDACTED]
[REDACTED]
[REDACTED]
[REDACTED]
[REDACTED]
- Overall PRO compliance rate is defined as: Total number of evaluable measurement/questionnaires across all scheduled assessment time, divided by total number of measurement/questionnaires expected to be received across all scheduled assessment time points multiplied by 100.
- Overall patient compliance rate is defined as: Total number of patients with an evaluable baseline and at least one evaluable follow-up measurement/questionnaire (as defined above), divided by the total number of patients expected to have completed at least a baseline measurement/questionnaire multiplied by 100.
- If feasible, compliance over time will be calculated separately for each scheduled assessment time, including baseline, as the number of patients with an evaluable questionnaire at the scheduled assessment time point (as defined above), divided

by number of patients still expected to complete questionnaires. Similarly, the evaluability rate over time will be calculated separately for each scheduled assessment, including baseline, as the number of evaluable questionnaires (per definition above), divided by the number of received questionnaires. For spirometry and oximetry, the scheduled assessments are collected daily by wearable device. Therefore, the daily compliance and daily evaluability rate will be calculated first and summarize as average over each time point defined in the Time Window in section 4.2.2.9.

4.2.4.8 Adverse Events

An AE for drugs is the occurrence of an undesirable medical condition or the deterioration of a pre-existing medical condition following or during exposure to a pharmaceutical product or device, whether or not considered causally related to the product or device. An AE for medical devices is any untoward medical occurrence, unintended disease or injury, or any untoward clinical signs (including an abnormal laboratory finding) in patients, users, or other persons whether or not considered related to the medical device. This includes events considered related to the medical device and events considered related to the study procedures involved. AEs will be collected throughout the study, from informed consent until 30 days after the End-of-Study visit.

Treatment-emergent adverse events (TEAEs) are defined as any AEs that occur or worsen at any time after the start of administration of the first dose of durvalumab and through 30 days after the last dose of durvalumab. Treatment-emergent AEs will be characterized based on the onset date relative to each patient's first dose date. For adverse events with incomplete start dates, the imputed dates will be used to determine whether the adverse events are treatment emergent.

Adverse events will be summarized by the SOC and PT based on the MedDRA dictionary version 22.1 or later. The CTCAE grades will be summarized by SOC and PT, using the current version of National Cancer Institute (NCI) CTCAE. For summaries by SOC and PT, a patient will be counted once at the SOC level and once at each PT within the SOC level. For

summaries by SOC, PT, and CTCAE Grade, a patient will be counted once at the highest grade for which the event occurred at the SOC level and the highest grade for each unique PT within that SOC level. Therefore, patients may only contribute once to each PT and once to each SOC level. The summaries presenting frequency of AEs by SOC and PT will be ordered by overall descending frequency of SOC and then, within a SOC, by overall descending frequency of PT.

The following AE tables will be provided:

- TEAEs, overall and by SOC and PT
- TEAEs related to pneumonitis by maximum relationship, overall and by SOC and PT
- TEAEs related to medical devices by maximum relationship, overall SOC and PT

With the exception of the overall summary AE table, only the TEAEs will be included in the summary tables; however, all AEs will be included in the listings. Any AE occurring before the first dose of durvalumab will be included in the data listings but will not be included in the summary tables of AEs.

Additional listings will be provided for deaths, AEs with an outcome of death, SAEs, AEs leading to discontinuation of durvalumab, study procedure and other significant AEs. TEAEs will be flagged in the listings. The death data will be listed in a separate listing.

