8.3.1.3 Adverse Events Information

AE and SAE collection will occur at Baseline (i.e., after the patient signs the ICF), during standard of care visits, at the End-of-Study visit, and for 30 days after the End-of-Study visit. The following information should be collected for AEs and SAEs reported to AZ or its delegate, Syneos Health Pharmacovigilance:

- AE (verbatim)
- The date (and time) when the AE started and stopped
- Intensity rating scale (intensity, maximum intensity or changes in intensity)
 - Mild
 - Moderate

- Severe

It is important to distinguish between serious and severe AEs. Severity is a measure of intensity whereas seriousness is defined by the criteria in [Section 8.3.1.1](#). An AE of severe intensity need not necessarily be considered serious. For example, nausea that persists for several hours may be considered severe nausea, but not an SAE unless it meets the criteria shown in [Section 8.3.1.1](#). On the other hand, a stroke that results in only a limited degree of disability may be considered a mild stroke but would be an SAE when it satisfies the criteria shown in [Section 8.3.1.1](#). The severity (i.e., grade) of all AEs will be documented at Baseline, during standard of care visits, and through final resolution (or other final outcome). When possible, the severity of Baseline conditions (i.e., AE-related signs/symptoms, laboratory measurements) will also be documented.

- Whether AE is serious or not
- Physician causality against durvalumab
- Action taken with regard to durvalumab
- Outcome

In addition, the following variables should be collected for SAEs reported to AZ (or its delegate, Syneos Health Pharmacovigilance, as described in [Sections 8.3.1.4](#) and [8.3.1.5](#), as applicable):

- Date site physician became aware of SAE
- Date AE met criteria for SAE
- The reason AE is serious
- Date of hospitalization
- Date of discharge
- Date of death
- Autopsy performed

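### An AE that starts between consent and first dose, worsens on durvalumab and stays in one record is a TEAE by the SAP's definition but not by its classification rule

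*SAP*

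**What the plan says.** The relevant rules stand close together in SAP 4.2.4.8.

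- **Definition.** TEAEs are "defined as any AEs that occur or worsen at any time after the start of administration of the first dose of durvalumab", up to 30 days after the last dose. Protocol 8.3.1.1 also includes worsening in its definition.
- **Classification.** The next sentence reads "Treatment-emergent AEs will be characterized based on the onset date relative to each" patient's first dose date. For AEs with incomplete start dates, "the imputed dates will be used to determine whether the adverse events are treatment emergent".
- **Tables.** "With the exception of the overall summary AE table, only the TEAEs will be included in the summary tables". The section goes on: "Any AE occurring before the first dose of durvalumab will be included in the data listings but will not be included in the summary tables". All AEs are to be listed, with TEAEs flagged.
- **Collection.** "AEs will be collected throughout the study, from informed consent until 30 days after the End-of-Study visit". SAP 3.1 allows Day 1 (first dose) to fall on the day of consent or up to two weeks later, so AEs with pre-dose onset can be on file.

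Protocol 8.3.1.3 lists among the data to be collected for an AE "Intensity rating scale (intensity, maximum intensity or changes in intensity"), and says that grade is documented at Baseline, at standard of care visits and until the event reaches its final outcome. SAP section 6, on changes from the protocol, does not mention a narrower TEAE rule.

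**The concern.** The definition has two routes into TEAE status, onset and worsening. The classification rule provides only the first. No worsening date, comparison with the pre-dose grade, or requirement to open a new record when the grade rises appears in the SAP. The exclusion of pre-dose AEs from the tables has no exception for events that later worsen.

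A programmer who follows the text literally will therefore classify some events as not treatment-emergent although the SAP's own definition says that they are. The listings do not repair this, because the TEAE flag rests on the same onset comparison. The study is descriptive and plans 75 patients, so the AE counts are themselves the safety result.

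The content of the overall AE table is also unclear. One sentence exempts it from the restriction to TEAEs, and the next excludes pre-dose AEs from the AE summary tables without saying whether the overall table is among them.

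**Working it through.** The plan states no figure for this point, so there is none to reproduce. The check applies the definition and the classification rule to the same hypothetical records. Days are counted from the first dose, and all events lie inside the TEAE window.

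**Inputs**

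- Definition, classification rule and pre-dose exclusion: SAP 4.2.4.8.
- Consent to first dose, 0 to 14 days: SAP 3.1.
- Planned number of patients, 75: SAP 1.3 and Protocol 9.1.

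**Rules as applied**

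- Definition: TEAE if onset is on or after first dose, or worsening is on or after first dose.
- Classification: TEAE if onset is on or after first dose.

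| Record | By definition | By onset rule |
|---|---|---|
| A. Onset 7 days before first dose, no worsening | not TEAE | not TEAE |
| B. Onset 7 days before first dose, worsens 20 days after, one record | TEAE | not TEAE |
| B-split. As B, but the worsening is a second record with onset 20 days after | TEAE | TEAE |
| C. Onset 10 days after first dose | TEAE | TEAE |
| D. Onset 10 days after, worsens 20 days after | TEAE | TEAE |

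The two rules disagree only for record B, which the pre-dose exclusion also keeps out of the summary tables. In these cases the onset rule never admits a record that the definition rejects, so any error is an undercount.

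**Size per patient**

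For one preferred term, the loss in incidence is k/75, where k is the number of patients whose only qualifying record of that term is of type B. The documents give no value for k. The values below are assumptions that show the scale; they are not estimates.

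- k = 0: 0.0 points
- k = 1: 1/75 = 1.3 points
- k = 2: 2/75 = 2.7 points
- k = 3: 3/75 = 4.0 points
- k = 5: 5/75 = 6.7 points

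The k = 1 value agrees with the one-event row of Protocol Table 4 (1.3%). SAP 4.2.4.8 counts a patient once per preferred term, so a patient with another post-dose record of the same term is still counted and does not enter k.

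**The case against.** **Record structure.** The strongest objection is that worsening may already produce a new record. SAP 4.2.1 and 4.2.2.1 describe the highest grade as belonging to an AE within an episode that may come later than the first one. SAP 4.2.2.2 allows the start and the resolution of an event to carry different AE numbers. If each grade increase opens a record with its own onset date, the onset rule does capture worsening (record B-split). This is plausible, and it is why the loss cannot be called certain. But neither document requires a new record, and the data items in Protocol 8.3.1.3 fit one record followed over time just as well.

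**Meaning of the onset sentence.** It does not say onset alone. That is correct; the reading is an inference from the absence of any other criterion, supported by the incomplete-date rule, which also works on start dates.

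**The two table sentences.** A reader might infer that they contradict each other. The documents do not firmly support that. TEAEs end 30 days after the last dose, whereas AE collection runs to 30 days after the End-of-Study visit. The exemption could therefore admit late AEs to the overall table while pre-dose AEs stay out. What stands is an ambiguity: the list of planned tables names no table of all AEs that would settle it.

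**Consequence.** The pneumonitis and pulmonary AE analyses have their own rules counted from Day 1. Every AE is listed, and deaths, SAEs and AEs leading to durvalumab discontinuation have separate listings. This limits the importance of the point but does not make the TEAE tables follow their definition.

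**Conclusion.** The definition and the classification rule in SAP 4.2.4.8 do not match. Read as written, they leave one kind of event out of the TEAE tables and without a TEAE flag: onset between consent and first dose, worsening on durvalumab, held as one record. The size is about 1.3 points on the affected term for each such patient, subject to the once-per-term counting rule. It assumes a denominator of 75; the actual safety analysis set may differ.

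Three stronger readings are tempting, and the documents do not support them:

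- *AEs that worsen on durvalumab drop out in general.* Every AE with onset after the first dose stays in. Deterioration of a pre-existing condition falls within the AE definition and can be a new AE with post-dose onset.
- *Chemoradiotherapy toxicity of Grade 2 or below, permitted at entry, enlarges the exposed group.* Toxicity already present at entry predates consent, so it is a baseline condition and not an AE with onset between consent and first dose.
- *A material number of patients is lost.* No figure in either document bears on how many AEs start in this window and then worsen, and zero is possible.

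The conclusion rests on the absence of any stated rule for worsening. If the CRF instructions require a new AE record at each grade increase, no events are lost, and one sentence in the SAP saying so would settle the classification issue.

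**What to change.** Three changes to SAP 4.2.4.8:

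1. Replace the onset sentence with a rule that covers both routes, for example: *An AE is treatment-emergent if its onset, or its first increase in CTCAE grade over the pre-dose grade, whether in the same or a new record, falls on or after the first dose and within the TEAE window.*
2. Limit the pre-dose exclusion from the summary tables to AEs that begin before the first dose and do not worsen after it.
3. Say whether the overall summary AE table includes non-TEAEs and, if so, whether these are pre-dose AEs, AEs after the TEAE window, or both.

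The TEAE flag in the listings should use the same derivation.

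The cost is SAP wording and one derivation from intensity data that Protocol 8.3.1.3 already plans to collect. No study procedure changes.
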